7.2 Medical History and Prior and Concomitant Medications

Medical history data will be coded using the Medical Dictionary for Regulatory Activities (MedDRA). The actual version of the MedDRA coding dictionary will be noted in the statistical tables and clinical study report. The number and percentage of subjects in each medical history category (by MedDRA system organ class and preferred term) will be summarized overall and for Study 1 and Study 2 subgroups for the WAS. The system organ class (SOC) will be presented in alphabetical order, and the preferred terms will be presented in alphabetical order within each SOC. Subjects reporting more than one PT within a SOC will be counted only once for that SOC. No statistical comparison will be performed for medical history reporting.

Concomitant medications during the Withdrawal Period and the Re-treatment Period will be summarized for the WAS and RAS respectively. Generally concomitant medications are those medications, other than study drug, taken after the first dose of study drug and within 1 day of the last dose of study drug. This includes medications with a start date between first study drug administration and last study drug administration + 1 day, as well as medications with a start date prior to first dose of study drug and which are ongoing after first dose of study drug. Medications taken on the day of the first dose of study drug

are counted as concomitant medications. For the purposes of Withdrawal Period summary, medications other than upadacitinib taken on or after Week 104 visit during treatment withdrawal will be considered as concomitant medications.

7.3 Protocol Deviations

Protocol deviations for Remission-Withdrawal study are described in [Appendix B](#).

8.0 Handling of Potential Intercurrent Events

For the Withdrawal Period, the potential intercurrent event is upadacitinib re-treatment. The following strategies will be used to handle the intercurrent event in efficacy analysis:

- For time-to-flare endpoint, the composite strategy will be used. Subjects who receive upadacitinib re-treatment without meeting disease flare criterion will be considered flared at the time of first dose.
- For binary endpoints, the composite strategy will be used to handle intercurrent events. Subjects who receive upadacitinib re-treatment will be considered as non-responder for all Withdrawal Period visits after first dose date.
- For continuous endpoints, the hypothetical strategy will be used to handle intercurrent events. All data after first dose date of upadacitinib re-treatment will be excluded from analysis and will be implicitly imputed by the statistical model.

For the Re-treatment Period, the potential intercurrent event is premature discontinuation of re-treatment study drug. The following strategy will be used to handle the intercurrent event in efficacy analysis:

- For all endpoints, the treatment-policy strategy will be used to handle intercurrent events. All collected efficacy data will be used as observed, regardless of whether the subject discontinued re-treatment study drug prior to the completion of the Re-treatment Period.

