 - History of inflammatory arthritis of different etiology other than axial SpA (including but not limited to RA, PsA, mixed connective tissue disease, systemic lupus erythematosus, reactive arthritis, scleroderma, polymyositis, dermatomyositis), or any arthritis with onset prior to 17 years of age;
 - Fibromyalgia (currently with active symptoms);
 - Extra-articular manifestations (e.g., psoriasis, uveitis, or inflammatory bowel disease) that are not clinically stable for at least 30 days prior to study entry.
- ✓ 29. There must be no reason the Investigator believes that the subject is an unsuitable candidate to participate in the study or receive study drug or would place the subjects at risk by participating in the study.

Remission-Withdrawal Period Specific Criteria:

- ✓ 30. Subject must be on study drug upon completion of the Open-Label Extension Period of Study 1 or Study 2 through Week 104.
- ✓ 31. Subject must achieve ASDAS (CRP) < 1.3 at Week 104 and ASDAS (CRP) < 2.1 at Week 88.
- ✓ 32. Subject must voluntarily sign and date an informed consent to participate in the Remission Withdrawal Period, approved by an IEC/IRB.
- ✓ 33. Subject must not have a newly suspected/acquired medical condition and/or initiate a new medication since the last dose of study drug that would have precluded his/her enrollment into the main study.
- ✓ 34. There must be no reason the Investigator believes that the subject is an unsuitable candidate to participate in the remission-withdrawal period or receive study drug or would place the subjects at risk by continuing to participate in the study.
- ✓ 35. Subjects must be willing to keep background axSpA medications stable during the Remission-Withdrawal Period (including withdrawal and re-treatment phases, if applicable).

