5.3 Prohibited Medications and Therapy

JAK Inhibitors

Prior and concomitant oral and topical exposure to any other JAK inhibitors (including but not limited to the investigational drug, upadacitinib [Rinvoq®]; tofacitinib [Xeljanz®]; baricitinib [Olumiant®]; filgotinib; ruxolitinib [Jakafi®]; abrocitinib [PF-04965842]; and peficitinib [Smyraf®]) is not allowed.

Targeted Biologic Therapies

Concomitant biologic therapies and biosimilar versions of biologic drugs are prohibited during treatment with study drug and in the Remission-Withdrawal Period. Examples of biologic therapies include but are not limited to the following:

- Abatacept
- Adalimumab
- Anakinra
- Belimumab
- Bimekizumab
- Certolizumab pegol
- Dupilumab
- Efalizumab
- Etanercept
- Golimumab
- Guselkumab
- Infliximab
- Ixekizumab

- Natalizumab
- Rituximab
- Risankizumab
- Secukinumab
- Tildrakizumab
- Tocilizumab
- Ustekinumab

Other Non-Biologic Systemic Therapy

Initiation of additional systemic immunomodulating therapy for the treatment of axSpA is prohibited during treatment with study drug outside of rescue parameters (refer to Section 5.4) and in the Remission-Withdrawal Period.

Corticosteroids

Spinal/paraspinal and SI joint injection(s) or parenteral administration of corticosteroids (including intramuscular and intravenous injections) or prednisone (or oral corticosteroid equivalents) > 10 mg/day are not allowed during treatment with study drug outside of rescue parameters (refer to Section 5.4) and in the Remission-Withdrawal Period; the following exceptions apply: short-term use (≤ 10 days) of corticosteroids for conditions that are not related to axSpA, such as exacerbation of asthma or chronic obstructive pulmonary disease, allergic reactions, or serious infection when additional corticosteroids may be required to prevent adrenal insufficiency, a total of up to 100 mg of prednisolone or equivalent is allowed during each study.

Investigational Drugs

Subjects who have been treated with any investigational drug within 30 days or 5 half-lives of the drug (whichever is longer) prior to the first dose of study drug are excluded from participation in the studies. Investigational drugs are also prohibited during the studies including the Remission-Withdrawal Period.

Vaccines

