 - MTX, SSZ, hydroxychloroquine, chloroquine, leflunomide, apremilast (concomitant use of up to 2 csDMARDs except the combination of MTX and leflunomide); and/or
 - Prednisone (≤ 10 mg/day) (or oral corticosteroid equivalent) and/or a corticosteroid burst with no more than 3 consecutive days of systemic corticosteroids (including intramuscular and intravenous injections) (maximum dose of 0.5 mg/kg/day of prednisone or its equivalent).
 - Subjects may continue concomitant use of study drug if background medications remain within allowed parameters (refer to Section 5.4, Allowed Therapies).

OR

2. Modify axSpA medications per standard of care (per local label) **with** initiation of a bDMARD:
 - TNF inhibitor or IL-17 inhibitor.
 - Subjects must permanently discontinue study drug prior to initiation of the bDMARD therapy for safety reasons (refer to Section 5.3 and Section 5.5).

[figure not shown]
Investigator or site staff will determine the subjects' ASAS20 response based on the values presented in the data capture systems.

After Week 52 (e.g., at Week 64 through Week 104 visits), addition or modification of axSpA medications listed above can be made per Investigator judgment regardless of the disease activity status (Figure 3).

Disease Activity Criteria for Permanent Study Drug Discontinuation:

At Week 64 and through Week 104, subjects without an ASAS20 response at any 2 consecutively scheduled visits will be permanently discontinued from study drug treatment (e.g., Week 52 and Week 64 with discontinuation at Week 64; or at Week 76 and Week 88 with discontinuation at Week 88), unless an alternative etiology exists to influence the individual domains of the ASAS20 response criteria (such as trauma, injury, or infection affecting the subject's ability to accurately perform pain, function, or global self-assessments of axial SpA disease activity) as documented by the Investigator (Figure 3).

Figure 3. Study 2 (nr-axSpA): Rescue Therapy and Permanent Study Drug Discontinuation Parameters

Background Medication During Remission-Withdrawal Period:

Starting at Week 104, subjects entering the Remission-Withdrawal Period, should keep their axSpA related background medication stable (including withdrawal and retreatment phases, as applicable).

COVID-19 Pandemic-Related Vaccination Guidance

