5.6 Follow-Up for Subject Withdrawal from Study

Discontinuation of Study Drug and Continuation of Study Participation

If a subject prematurely discontinues study drug, the procedures outlined for a Premature Discontinuation Visit (PD Visit) should be completed as soon as possible, preferably within 2 weeks, and preferably prior to initiation of another therapy. To minimize missing data for efficacy and safety assessments, subjects who prematurely discontinue study drug treatment should continue to be followed for all regularly scheduled visits as outlined in the Activity Schedule ([Appendix D](#)) and adhere to all study procedures except for dispensing study drug, PK sample collection, and blood sample collection for optional biomarker research studies, unless subjects have decided to discontinue study participation entirely (withdrawal of informed consent). In addition, all efficacy-driven criteria for addition or modification of background medications and study drug discontinuation no longer apply. If at any point a subject no longer wants to provide assessments (withdrawal of informed consent) following discontinuation of study drug, a second PD Visit is not required. Subjects should be advised on the continued scientific importance of their data even if they discontinue treatment with study drug early. Following discontinuation of study drug, the subject should be treated in accordance with the Investigator's best clinical judgment irrespective of whether the subject decides to continue participation in a study.

Premature Discontinuation of Study (Withdrawal of Informed Consent)

If a subject prematurely discontinues study participation (withdrawal of informed consent), the procedures outlined for the PD Visit should be completed as soon as possible, preferably within 2 weeks, and preferably prior to initiation of another therapy. In addition, if subject is willing, a 30-day F/U Visit (or phone call) after the last dose of study drug may be completed to determine the status of any ongoing AEs/SAEs or the occurrence of any new AEs/SAEs.

For subjects to be considered lost to follow-up, reasonable attempts must be made to obtain information on the subject's final status. At a minimum, 2 telephone calls must be made and 1 certified letter must be sent and documented in the subject's source documentation.

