For multiplicity-controlled secondary continuous efficacy variables, additional sensitivity analysis will be conducted corresponding the treatment policy estimand, where missing data will be imputed using Multiple Imputation. The imputation model will include demographics variables and Baseline disease characteristics, as well as longitudinal response observed at any other visits. The analysis of covariance (ANCOVA) model will be performed on each of the multiple imputed datasets adjusting for treatment, main stratification factor, and Baseline value. The ANCOVA results from the multiple imputed datasets will be combined using the Rubin's method.

Additional Efficacy Analyses

Additional efficacy variables will be summarized for all visits. For efficacy analysis of the placebo-controlled period (up to Week 14 in Study 1 [bDMARD-IR] and Week 52 in Study 2 [nr-axSpA]), similar statistical methods as for the primary and secondary endpoints will be used. For binary endpoints, comparisons between the upadacitinib group and the placebo group will be performed using the CMH test adjusting for the main stratification factor. Corresponding to the composite estimand, subjects who discontinue study drug or use rescue medication will be treated as non-responders for visits after study drug discontinuation or initiation of rescue medication. Missing data will be imputed similarly as for the primary endpoint. A sensitivity analysis will be conducted where all missing data are treated as non-responders. For continuous endpoints, comparisons between the upadacitinib group and the placebo group will be performed using the MMRM with treatment group, visit, and treatment-by-visit interaction as fixed effects and the corresponding Baseline value and the main stratification factor as the covariates. Handling of data observed after rescue will be further detailed in the SAP.

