Long-term efficacy analysis will be performed similarly as described above, corresponding to the composite estimand for binary endpoints and the treatment policy estimand for continuous endpoints. For binary endpoints, supplementary analysis using the treatment policy estimand may also be conducted on all data as observed. For efficacy analysis beyond the placebo-controlled period (Week 14 in Study 1 [bDMARD-IR] and Week 52 in Study 2 [nr-axSpA]), no statistical comparison will be performed; descriptive statistics and 95% CIs will be provided. The analyses will be performed by randomized treatment sequence as described below:

1. Placebo → upadacitinib 15 mg QD
2. Upadacitinib 15 mg QD → upadacitinib 15 mg QD

Efficacy Analysis for the Remission-Withdrawal Period

For time to flare during the withdrawal period, the Kaplan-Meier (KM) curve will be provided based on as observed data. Subjects who discontinue the Remission-Withdrawal Period (prior to observed flare) will be considered censored. Subjects who receive retreatment will be considered flared. The KM estimator and associated 95% CIs for the flare-free rate during the withdrawal period will be provided. Similar analyses will also be performed for time to flare between Week 52 and Week 104 for Study 1 and Study 2 as well as for M16-098 (SELECT-AXIS 1).

For analysis of binary endpoints at scheduled visits during the withdrawal period, non-responder imputation will be used, where subjects who flare, discontinue the study, or have missing values are considered non-responders. For analysis of continuous endpoints, MMRM will be used. For all endpoints, analysis based on as observed data will also be performed. Descriptive statistics and 95% CIs will be provided. Data after retreatment will be excluded from these analyses and analyzed separately.

For subjects who receive re-treatment of upadacitinib after disease flare, analysis of endpoints after re-treatment will be based on data as observed. Change from baseline and improvement response are calculated from the retreatment baseline. Descriptive statistics and 95% CIs will be provided.

Subgroup Analysis for Efficacy

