TB test (QuantIFERON TB Gold test [or interferon gamma release assay equivalent such as T-SPOT test] and/or local PPD skin test, if required)	✓												✓				✓			
HBV (post-Baseline tests for subjects from Japan only)	✓						✓			✓	✓	✓	✓	✓	✓	✓	✓		✓	
HLA-B27		✓																		
Study 1 (bDMARD-IR AS) blood samples for upadacitinib PK assay (only in approximately 30% of subjects in select sites)				✓		✓	✓	✓											✓	
Study 2 (nr-axSpA) blood samples for upadacitinib PK assay (only in approximately 30% of subjects in select sites)				✓		✓		✓		✓		✓							✓	
 TREATMENT																				
Randomization/drug assignment		✓																		

Activity	Screening	Baseline	Wk 1	Wk 2	Wk 4	Wk 8	Wk 12	Wk 14	Wk 18	Wk 24	Wk 32	Wk 40	Wk 52	Wk 64	Wk 76	Wk 88	Wk 104	Unscheduled Visit	PD Visit	30-Day F/U Visit OR Phone Call
		Day 1																		
Dispense study drug		✓			✓	✓	✓	✓		✓	✓	✓	✓	✓	✓	✓		✓		
Dispense study drug (subjects entering OLE for applicable countries; see Appendix F)																	✓			

Optional Biomarker Sample Activities Table (Applicable for Study 1 and Study 2)

Activity	Screening	Baseline	Wk 1	Wk 2	Wk 4	Wk 8	Wk 12	Wk 14	Wk 18	Wk 24	Wk 32	Wk 40	Wk 52	Wk 64	Wk 76	Wk 88	Wk 104	Unscheduled Visit	PD Visit	30-Day F/U Visit OR Phone Call
		Day 1																		
Study 1 (bDMARD-IR AS) blood: (DNA/RNA/serum/plasma)		✓		✓				✓												
Study 2 (nr-axSpA) blood: (DNA/RNA/serum/plasma)		✓		✓				✓					✓							

Study Activities Table for Remission-Withdrawal Period (Prior to Retreatment)

Activity	Wk 110	Wk 116	Wk 122	Wk 128	Wk 140	Wk 152	Unscheduled Visit	PD Visit
INTERVIEWS & QUESTIONNAIRES								
Concomitant therapy	✓	✓	✓	✓	✓	✓	✓	✓
Review and document pregnancy avoidance recommendations with females of childbearing potential	✓	✓	✓	✓	✓	✓	✓	✓
PRO								
BASDAI, PtGA, Total Back Pain, BASFI, Patient's Global Assessment of Pain, Nocturnal Back Pain, ASAS HI	✓	✓	✓	✓	✓	✓	✓	✓
EXAM								
Body weight	✓	✓	✓	✓	✓	✓	✓	✓
Vital signs	✓	✓	✓	✓	✓	✓	✓	✓
Physical Exam				✓		✓		
AE assessment	✓	✓	✓	✓	✓	✓	✓	✓
Investigator assessments: TJC/SJC, BASMI _{in} , MASES, PGA	✓	✓	✓	✓	✓	✓	✓	✓
ASDAS (CRP) calculation to determine disease status	✓	✓	✓	✓	✓	✓	✓	
LOCAL LAB								
Erythrocyte sedimentation rate	✓	✓	✓	✓	✓	✓	✓	✓
Urine pregnancy test (for all female subjects of childbearing potential entering OLE for applicable countries; see Appendix F)						✓		

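### The Withdrawal Period flare-free rate can read too high after early exit or other systemic axSpA therapy, no time-to-flare sensitivity analysis would show it, and the flare threshold is stated two ways

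*SAP*

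**What the plan says.** **Intercurrent events.** SAP 8.0: "For the Withdrawal Period, the potential intercurrent event is upadacitinib re-treatment". A subject re-treated without meeting the flare criterion is counted as flared at the first dose, becomes a non-responder afterwards, and has later continuous data excluded. No other Withdrawal Period event has a rule.

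**Other therapy.** Protocol 5.3: "Concomitant biologic therapies and biosimilar versions of biologic drugs are prohibited during treatment with study drug and in the Remission-Withdrawal Period". The same section prohibits starting additional systemic immunomodulating treatment for axSpA. Entry criterion 35 in protocol 5.1 reads "Subjects must be willing to keep background axSpA medications stable during the Remission-Withdrawal Period", and protocol 5.4 says that subjects entering the period "should keep their axSpA related background medication stable". The SAP tabulates such use as concomitant medication (7.2) and as a protocol deviation (Appendix B).

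**Early leavers.** Protocol 7.3: "Subjects who discontinue the Remission-Withdrawal Period (prior to observed flare) will be considered censored". SAP 9.2.1.1 and 9.2.2 censor at the last flare assessment, whatever its value. Protocol 7.3 bases the curve on data as observed. Neither document plans a sensitivity analysis for time to flare.

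**Exit readings.** In the pre-retreatment table of protocol Appendix D, the row "ASDAS (CRP) calculation to determine disease status" is ticked at scheduled and unscheduled visits but not at the PD Visit, although the inputs to ASDAS are collected there. The SAP does not say whether such a reading is a flare assessment.

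**Flare threshold.** SAP 3.1 requires ASDAS (CRP) above 2.1 at two consecutive visits. SAP 2.2 and protocol 4.1 require at least 2.1. All add a single value above 3.5.

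**The concern.** The objective of this period is maintenance of disease control after withdrawal, and the KM curve is its only flare-free estimate. With no control arm, an error in the absolute rate is not cancelled by a comparison.

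A subject who is losing control and starts a biologic or another systemic agent may never reach two flare-level readings. That subject stays in the risk set as flare-free to Week 152, can count as a responder, and contributes later values to the MMRM.

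A subject who has one flare-level reading and leaves is censored at that reading. KM then assigns that subject the same future flare risk as those still in control, although a subject already at flare level is more likely to be confirmed at the next visit. For binary endpoints the same leaver is a non-responder (SAP 9.2.1.2), so the two endpoint types treat one subject in opposite ways.

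The two thresholds classify a reading of exactly 2.1 differently. Because ASDAS low disease activity is defined as below 2.1, such a reading is neither low disease activity nor flare-level under SAP 3.1.

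**Working it through.** The documents give no sample size, flare rate, exit rate or other-therapy rate for this period, so there is no plan figure to reproduce. What follows is an illustration.

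**Inputs from the documents.** Visits at Weeks 110, 116, 122, 128, 140 and 152 (protocol Appendix D), that is 6, 12, 18, 24, 36 and 48 weeks after Week 104. Flare at the second consecutive flare-level reading. Leavers censored at the last assessment.

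**Assumptions.**
- The Week 152 confirmed-flare-free rate S, with no exits and no other therapy, is 30, 50 or 70%.
- The hazard of a lasting first crossing is constant, and no first reading exceeds 3.5.
- Confirmation comes at the next scheduled visit.
- A share q of subjects with a first flare-level reading before Week 152 leave at that reading.
- A share r of those losing control are held below threshold by other therapy and stay to Week 152.

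To be confirmed by Week 152, the first crossing must occur by Week 140 (36 weeks). The weekly hazard is therefore −ln(S)/36; for S = 50% it is 0.693/36 = 0.01925.

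**Route 1, exit after one reading.** For S = 50% and q = 10%, per 100 subjects:

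| First reading | First crossers | Leave, censored | At risk at next visit | Confirmed there | Factor | KM |
|---|---|---|---|---|---|---|
| Week 110 | 10.91 | 1.09 | 98.91 | 9.82 | 0.9007 | 0.9007 |
| Week 116 | 9.72 | 0.97 | 88.12 | 8.75 | 0.9007 | 0.8113 |
| Week 122 | 8.66 | 0.87 | 78.50 | 7.79 | 0.9007 | 0.7308 |
| Week 128 | 7.71 | 0.77 | 69.94 | 6.94 | 0.9007 | 0.6582 |
| Week 140 | 13.00 | 1.30 | 61.70 | 11.70 | 0.8104 | 0.5334 |

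Each factor is 1 − confirmed/at risk. The planned KM reads 53.3% instead of 50%, or +3.3 points. The same calculation for the other cases gives:

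| Unconfirmed leavers among first crossers | Share of all subjects, q × (1 − S) | Excess at S = 30/50/70% (points) |
|---|---|---|
| 0% | 0 | 0 |
| 5% | 3.5/2.5/1.5% | +1.6/+1.6/+1.2 |
| 10% | 7/5/3% | +3.4/+3.3/+2.5 |
| 20% | 14/10/6% | +7.3/+7.0/+5.0 |

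The excess depends on leavers who have no confirming reading. If 10% leave and half of them have a confirming PD reading, the unconfirmed share is 5% and the second row applies (confirmation placed at the next grid visit). If all are confirmed, the excess is 0. If 30% or 50% of first crossings exceed 3.5, and so are flares at once, the 10% case falls to +2.3/+2.2/+1.6 or +1.6/+1.5/+1.1.

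Counting the unconfirmed leavers as events at their single reading returns the Week 152 rate to S in this model, because nobody is then censored before Week 152.

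**Route 2, other therapy.** With no exits, the planned KM at Week 152 is S + r(1 − S). For r = 5%:
- 0.30 + 0.05 × 0.70 = 0.335 (+3.5 points)
- 0.50 + 0.05 × 0.50 = 0.525 (+2.5 points)
- 0.70 + 0.05 × 0.30 = 0.715 (+1.5 points)

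This is 1 point for each 1% of all subjects affected.

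**The case against.** **A reader might infer that the plan is silent on other therapy.** It is not quite. Data as observed (protocol 7.3) means that values after other therapy are used as measured, which is in effect treatment policy. The SAP does not say so, but the default can be read. Whether a composite rule is better for the main curve is open to debate.

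**Other therapy is prohibited, so it is a deviation and not an expected pathway.** That stands as far as frequency goes, which may be low. The protocol rule for the placebo-controlled period, under which "subjects who discontinue study drug or use rescue medication will be treated as non-responders", concerns rescue that the protocol itself directs, so it is not a strict precedent. The closer parallel is in SAP 8.0, where re-treatment without a met flare criterion is already counted as a flare. A prohibition still does not say how the data are analysed once it is broken.

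**A reader might infer that the PD Visit comes too early to confirm a flare.** Protocol 5.6 says "the procedures outlined for the PD Visit should be completed as soon as possible, preferably within 2 weeks", but that interval runs from discontinuation, not from the last ASDAS. Scheduled visits are 6 to 12 weeks apart, and SAP 2.2 judges consecutive visits on observed records. An exit reading can therefore confirm a flare if it is allowed to count. An unticked calculation row does not show that it is excluded.

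**Existing outputs already help.** SAP 5.0 counts premature discontinuations in this period, overall and by study, which caps the number of leavers. ASDAS low disease activity with non-responder imputation treats leavers as failures. Both stand, but neither shows the effect on the KM curve, and the second does not cover other therapy.

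**Conclusion.** The point holds as a possible upward bias that no planned time-to-flare analysis would reveal. It arises only if leaving or starting therapy is related to loss of control. If neither event occurs, or if every leaver has a confirming reading that counts, it is zero. The illustrated excess is 1.2 to 3.4 points for 10% leavers, depending on S and on whether none or half are confirmed, and 1.5 to 3.5 points for 5% on other therapy. All these rates are assumptions, so confidence applies to the text and the direction, not to the size.

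Two stronger readings are not supported. No test or claim is threatened: time to flare is an additional endpoint (protocol 3.4), the analyses are descriptive (SAP 9.1), and there is no formal testing (SAP 13.0). Nor does a first flare-level reading at Week 152 bias the endpoint, because the endpoint is confirmed flare.

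The threshold discrepancy is a plain contradiction, though probably small in effect. It matters only for readings of exactly 2.1, and a subject re-treated under one definition who does not meet the other is still counted as flared at first dose by SAP 8.0.

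**What to change.** 1. Keep the KM with the protocol's censoring as the main analysis, and state in the SAP that data after other therapy are used as observed in it.
2. In SAP 9.2.2 add one sensitivity KM in which:
   - an unconfirmed flare-level ASDAS at the last assessment before early exit is an event at that visit; and
   - initiation or escalation of systemic axSpA therapy is an event at its start date, as SAP 8.0 does for re-treatment. Exclude the peripheral injections permitted in protocol 5.4 and the short steroid courses for other conditions permitted in protocol 5.3.

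   Completers with a single flare-level reading at Week 152 stay censored.
3. State that ASDAS readings at PD and unscheduled visits count as flare assessments when at least 2 weeks after the first.
4. Reconcile the flare threshold in SAP 3.1 with SAP 2.2 and protocol 4.1.

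**Cost.** SAP wording and a little programming. Concomitant therapy and the ASDAS inputs are already collected at every withdrawal visit, including unscheduled and PD visits. The sensitivity rate may be lower than the main one, because some transient rises and some therapy starts in subjects who would not have flared will count as flares. For therapy starts this is up to 1 point per 1% of subjects. That is why it belongs beside the main curve and not in its place.
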